- sSOL: estimated minutes from the time the subject attempted to sleep until sleep onset
- sWASO: sum of estimated minutes of wake during the night after initial sleep onset until the time the subject stopped trying to sleep for the night
- sTST: derived minutes of sleep from sleep onset until the time the subject stopped trying to sleep for the night
- sSE: proportion of sTST per subjective time spent in bed, calculated as the interval from the time the subject reported attempting to sleep until the time the subject stopped trying to sleep for the night, and time spent asleep derived from time spent in bed minus sWASO (revised per Amendment 03)

Quality of Sleep and Morning Sleepiness

The Sleep Diary will be used to assess the subject's global perception of quality of sleep on the previous night with the following question: "How would you rate the quality of your sleep last night?" Subjects will rate the quality of their sleep on a scale from 1 to 9, with 1 being extremely poor and 9 being extremely good.

The Sleep Diary will be used to assess subjective ratings of morning sleepiness with the following question: "How sleepy/alert do you feel this morning?" Subjects will rate their sleepiness/alertness level on a scale from 1 to 9, with 1 being extremely poor and 9 being extremely good.

Alcohol Consumption

The Sleep Diary will include questions that ask about alcohol consumption the previous day, including within 3 hours before bedtime and/or exceeding the daily maximum of 2 alcoholic drinks per day.

ISI

The ISI is a 7-item, self-report questionnaire assessing the nature, severity, and impact of insomnia. The dimensions evaluated are severity of: sleep onset, sleep maintenance, early-morning awakening problems; sleep dissatisfaction; interference of sleep difficulties with daytime functioning, noticeability of the sleep problems by others; and distress caused by the sleep difficulties. A 5-point Likert scale is used to rate each item (from 0=no problem to 4=very severe problem) yielding a total score from 0 to 28.

FSS

The FSS is a self-report scale on which subjects are instructed to choose a number from 1 to 7 that indicates their degree of agreement with each of 9 statements about their fatigue where "1" indicates strongly disagree and "7", strongly agree. The FSS score is the sum of all responses to the 9 questions. Higher scores indicate greater fatigue.

Pharmacokinetic Assessments

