9.3.1 Inclusion Criteria

Subjects must meet all of the following criteria to be included in this study:

1. Male or female, age 18 years or older at the time of informed consent
2. Meets the Diagnostic and Statistical Manual of Mental Disorders, Fifth Edition (DSM-5) criteria for Insomnia Disorder, as follows:
 - Complains of dissatisfaction with nighttime sleep in the form of difficulty getting to sleep, difficulty staying asleep and/or awakening earlier in the morning than desired despite adequate opportunity for sleep
 - Frequency of complaint ≥ 3 times per week
 - Duration of complaint ≥ 3 months
 - Associated with complaint of daytime impairment
3. At Screening: History of sSOL ≥ 30 minutes on at least 3 nights per week in the previous 4 weeks AND/OR sWASO ≥ 60 minutes on at least 3 nights per week in the previous 4 weeks (revised per Amendment 03)
4. At Screening: Reports regular time spent in bed, either sleeping or trying to sleep, between 7 and 9 hours

5. At 1st Screening Visit (Visit 1) and 2nd Screening Visit (Visit 2a): Reports regular bedtime, defined as the time the subject attempts to sleep, between 21:00 and 01:00 and regular waketime, defined as the time the subject gets out of bed for the day, between 05:00 and 10:00 (revised per Amendment 03)
6. At Screening and Study Baseline: ISI score ≥ 15
7. At the 2nd Screening Visit (Visit 2a): Confirmation of current insomnia symptoms as determined from responses on the Sleep Diary completed on at least 7 consecutive mornings (minimum 5 of 7 for eligibility), such that sSOL ≥ 30 minutes on at least 3 of the 7 nights and/or sWASO ≥ 60 minutes on at least 3 of the 7 nights (revised per Amendment 03)
8. At the 2nd Screening Visit (Visit 2a): Confirmation of regular bedtimes and waketimes, as determined from responses on the Sleep Diary completed on a minimum of 7 consecutive mornings between the 1st and 2nd screening visit, such that the subject has a regular time spent in bed, either sleeping or trying to sleep, between 7 and 10 hours (revised per Amendment 03)
9. At the 2nd Screening Visit (Visit 2a): Confirmation of sufficient duration of time spent in bed, as determined from responses on the Sleep Diary completed on 7 mornings between the 1st and 2nd screening visit, such that there are not more than 2 nights with duration of time spent in bed < 7 hours or > 10 hours (revised per Amendment 03)

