9.5.1.3 Efficacy Assessments

9.5.1.3.1 ELECTRONIC SLEEP DIARY

An electronic sleep diary was developed for the purposes of the Phase 3 clinical program. Subjects must comply with requirements for completion of the sleep diary. Failure to comply will require discussion with the Medical Monitor and may result in discontinuation of the subject from the study.

The Sleep Diary will be completed within an hour of morning waketime on each morning of the study from Screening through the end of the Follow-Up Period. This Sleep Diary will yield several self-reported measures of sleep that will be used to determine eligibility, as well as to assess efficacy. In addition, the Sleep Diary will include questions that relate to morning sleepiness and to alcohol consumption. (revised per Amendment 03)

SLEEP PARAMETERS

- sSOL: estimated minutes from the time the subject attempted to sleep until sleep onset

- sWASO: sum of estimated minutes of wake during the night after initial sleep onset until the time the subject stopped trying to sleep for the night
- sTST: derived minutes of sleep from sleep onset until the time the subject stopped trying to sleep for the night
- sSE: proportion of sTST per subjective time spent in bed, calculated as the interval from the time the subject reports attempting to sleep until the time the subject stopped trying to sleep for the night, and time spent asleep derived from time spent in bed minus sWASO (revised per Amendment 03)

QUALITY OF SLEEP AND MORNING SLEEPINESS

The Sleep Diary will be used to assess the subject's global perception of quality of sleep on the previous night with the following question: "How would you rate the quality of your sleep last night?" Subjects will rate the quality of their sleep on a scale from 1 to 9, with 1 being extremely poor and 9 being extremely good.

The Sleep Diary will be used to assess subjective ratings of morning sleepiness with the following question: "How sleepy/alert do you feel this morning?" Subjects will rate their sleepiness/alertness level on a scale from 1 to 9, with 1 being extremely poor and 9 being extremely good.

ALCOHOL CONSUMPTION

The Sleep Diary will include questions that ask about alcohol consumption the previous day, including within 3 hours before bedtime and/or exceeding the daily maximum of 2 alcoholic drinks per day.

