3.1.2 Secondary Endpoints

The key secondary endpoints are:

- Mean change from Study Baseline in sSE at Month 6

- Mean change from Study Baseline of sWASO at Month 6

Additional secondary endpoints are:

- Mean change from Study Baseline of sSOL, of sSE, of sWASO and of sTST, at the beginning of treatment (mean of the 7 nights after the 1st dose in Period 1), at Month 1 and at Month 3
- Mean change from Study Baseline of sTST at Month 6
- Proportion of responders at Month 6 and Month 12, where sleep onset responder is defined as follows: sSOL at Study Baseline is ≥ 30 minutes and mean sSOL at 6 months is ≤ 20 minutes, and sleep maintenance responder is defined as follows: sWASO at Study Baseline is ≥ 60 minutes and mean sWASO at 6 months is ≤ 60 minutes and shows a reduction of >10 minutes compared to Study Baseline.
- Change from Study Baseline in daytime functioning, assessed as the total score from the 4 items on daytime functioning, on the ISI, at Months 1, 3, and 6
- Change from Study Baseline on the FSS at Months 1, 3, and 6
- Ratings on the morning sleepiness item of the Sleep Diary, for:
 - The mean change from Study Baseline of the 1st 7 mornings after the 1st dose in Period 1 and Period 2
 - The mean change from Study Baseline at: Month 1, Month 3, and Month 6
 - The mean change from Study Baseline and from Treatment Period 2 Baseline (as appropriate): for subjects with 1, 3, 6, 9 and 12 months exposure
 - The mean change from Screening for the 1st 7 mornings and 2nd 7 mornings of the Follow-up Period
- Rebound insomnia endpoints as assessed from the Sleep Diary during the Follow-up Period
 - Change from Screening of sSOL on each of the 1st 3 nights, mean sSOL of the 1st 7 nights, and mean sSOL of the 2nd 7 nights of the Follow-up Period
 - Change from Screening of sWASO on each of the 1st 3 nights, mean sWASO of the 1st 7 nights and mean sWASO of the 2nd 7 nights of the Follow-up Period
 - Proportion of subjects whose sSOL is longer than at Screening for each of the 1st 3 nights, or whose mean sSOL is longer than at Screening for 1st 7 nights or 2nd 7 nights of the Follow-up Period
 - Proportion of subjects whose sWASO is higher than at Screening for each of the 1st 3 nights, or whose mean sWASO is higher than at Study Baseline for the 1st 7 nights or 2nd 7 nights of the Follow-up Period
- Persistence of Effect
 - Mean change from Study Baseline of sSOL, of sSE, of sWASO and of sTST at Months 3, 6, 9, and 12 compared to Month 1

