3.3.5 Handling of Missing Data, Dropouts, and Outliers

This study collected sleep diary data directly from subjects via a vendor-provided hand-held device; it is possible that some values entered by subjects may have resulted from input errors. For example, it is not possible for a total waketime to be longer than the time the subject spends in bed for the night. In such cases, erroneous data will be considered as missing values in data analyses. Efficacy data handling will be mentioned in the [Section 6.1](#).

The primary and key secondary efficacy endpoints will be analyzed using mixed effect model repeated measurement analysis (MMRM), the missing values will be imputed using pattern-mixture multiple imputation (MI) assuming the missing data is missing not at random (MNAR) utilizing the complete case missing value pattern (CCMV). Additional sensitivity analyses will also be performed on primary and key secondary efficacy endpoints as follows:

Table 3 Multiple Imputation Methods

MI Methods	Assumption	Analysis Type																																																																
Complete Case Missing Value (CCMV)	Subjects with missing data at any day have a similar distribution as the completers within the respective treatment group (Pattern 1, below), where completers are defined as having no missing assessments for any post-baseline visits	Primary																																																																

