3.4.2.4 Other Secondary Efficacy Analyses

For all other secondary endpoints described below, the continuous variable will be summarized by using descriptive statistics by time point and the categorical variable will be summarized as the number and percentage of subjects by time point.

Unless is covered from the same model from the primary and secondary efficacy endpoints, or specified otherwise, the change from baseline assessments will be analyzed using MMRM assuming MAR (no missing value imputation) and the portion of responders will be analyzed using the Cochran Mantel Haenszel (CMH) test adjusted for region and age group. Missing values will be considered as non-responders in all responder analyses. No multiplicity adjustment will be made for all analyses.

The following endpoints will be analyzed.

EFFICACY MEASURES DERIVED FROM THE SLEEP DIARY

- Change from Study Baseline of mean sSOL, mean sSE, mean sWASO and mean sTST for the 1st 7 nights, Months 1, 2, 3, 4 and 5; and mean sTST at Month 6; for LEM5 and LEM10 compared to PBO
- Change from Study Baseline/ Treatment Period 2 Baseline of mean sSOL, mean sSE, mean sWASO and mean sTST for 1, 3, 6, 9 and 12 months exposure to LEM5 and LEM10. . Data from subjects randomized to LEM5 or LEM10 at the start of the study will use Study Baseline, data from subjects who were re-randomized to LEM5 or LEM10 in Period 2 will use Treatment Period 2 Baseline.
- The proportion of responders, separately for sSOL and sWASO, will be analyzed, for the first 7 nights, Months 1, 2, 3, 4, 5 and 6 for LEM5 and LEM10 compared to PBO:
 - The sleep onset responder is defined as: sSOL at Study Baseline is >30 minutes and mean sSOL at each month (first 7 nights, Months 1, 2, 3, 4, 5, 6) is ≤ 20 minutes,
 - The sleep maintenance responder is defined as: sWASO at Study Baseline is >60 minutes and mean sWASO at each month (first 7 nights, Months 1, 2, 3, 4, 5, 6) is ≤ 60 minutes and shows a reduction of >10 minutes compared to Study Baseline.

The proportion of responders will be analyzed based on the subjects with sSOL > 30 minutes at the baseline for sSOL and separately the subjects with sWASO > 60 minutes at the baseline for sWASO.

- The proportion of responders, separately for sSOL and sWASO, at Months 7, 8, 9, 10, 11 and 12 will also be summarized by using two types of baseline (ie., Study Baseline, Period 2 Baseline). The definition of the responder at Month 7, 8, 9, 10, 11 and 12 will be as follows:

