6.1.2 Derivation of Primary and Key Secondary Endpoints for Sleep Diary

Each Sleep Diary parameter will be derived by calculating the average of weekly (7 days) diary parameter values.

Baseline is the mean of diary data entered on the last 7 mornings during the Run-In Period before randomization; sleep diary parameter of the first 7 nights is the mean of diary data entered on the first 7 mornings following the start of treatment; sleep diary parameter for each visit is the mean of diary data entered on the last 7 mornings prior to that visit.

For the follow-up period, if the first 7 nights overlap with the last 7 nights (eg, the follow-up period is less than 14 days in total), the last non-overlap nights will be used in calculating the average value for the last 7 nights.

The following 7 questions are captured in the electronic Sleep Diary:

- Q1: What time did you try to go to sleep?
- Q2: How long did it take you to fall asleep?
- Q3: How many times did you wake up, not counting your final awakening?
- Q4: In total, how long did these awakenings last?
- Q5: What time was your final awakening?
- Q6: After your last awakening, how much longer did you try to sleep?
- Q7: What time did you get out of bed for the day?

The efficacy endpoints from electronic Sleep Diary are defined as follows:

- $sSOL = Q2$
- $sWASO = Q4 + (Q7 - Q5)$
- $sTST = TIB - \text{time spent awake}$ [where $TIB = Q7 - Q1$; and $\text{time spent awake} = Q2 + Q4 + Q7 - Q5$]
- $sSE = sTST/TIB$ (as defined above)

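### Protocol and SAP end sWASO and the sSE time-in-bed interval at different moments: giving up on sleep versus getting out of bed

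*Protocol*

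**What the plan says.** **Protocol.** Section 9.5.1.3.1 and the synopsis describe sWASO as the "sum of estimated minutes of wake during the night after initial sleep onset until the time the subject stopped trying to sleep". The sSE interval starts when the subject attempts to sleep and, in the synopsis wording, runs "until the time the subject stopped trying to sleep for the night, and time spent asleep derived from time spent in bed minus sWASO". The protocol does not print the diary items. It does treat leaving bed as an event with its own name: inclusion criterion 5 refers to "regular waketime, defined as the time the subject gets out of bed for the day".

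**SAP.** Section 6.1.2 lists seven diary items. Those that matter here are Q1 (time of trying to go to sleep), Q2 (time to fall asleep), Q4 (total duration of awakenings), Q5 (time of final awakening), Q6 ("After your last awakening, how much longer did you try to sleep") and Q7 ("What time did you get out of bed for the day"). The formulas are:

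- sSOL = Q2
- sWASO = Q4 + (Q7 − Q5)
- TIB = Q7 − Q1
- sTST = TIB − (Q2 + Q4 + Q7 − Q5)
- sSE = sTST/TIB

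Q6 appears in none of them. Neither SAP Section 5 nor the SAP's table of changes mentions a departure from the protocol definition.

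**The concern.** The sSE and sWASO changes at Month 6 are the last four of the six tests in the gate-keeping sequence (steps c to f in Protocol 9.7.1.6). A programmer following the SAP will compute values that differ from the protocol definition on every night when the subject stays in bed after giving up on sleep.

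The same sWASO feeds the sleep maintenance responder endpoint, which uses absolute 60-minute cut-offs. If the mismatch is found after the sponsor has seen Period 1 treatment codes, the choice between two derivations of confirmatory endpoints will be open to the charge that the data guided it.

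**Working it through.** **1. The plan's own sWASO figure.** Inputs from Protocol 9.7.2: difference 11.4 min, SD 43, two-sided alpha 0.05, 90% power. n per group = 2 × (1.960 + 1.282)² × 43² / 11.4² = 299, against 300 stated. The sample size arithmetic is sound. It rests on an SD of 43 from Study 201, and neither document says which derivation of sWASO produced that SD.

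**2. Matching the wording to the items.** Of the items the SAP lists, the closest match to the moment the subject stopped trying to sleep is Q5 + Q6, the final awakening plus the further time spent trying. The definitions then compare as follows.

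| | Protocol end point (Q5 + Q6) | SAP end point (Q7) |
|---|---|---|
| sWASO | Q4 + Q6 | Q4 + Q7 − Q5 |
| Time in bed | Q5 + Q6 − Q1 | Q7 − Q1 |
| sTST | Q5 − Q1 − Q2 − Q4 | Q5 − Q1 − Q2 − Q4 |
| sSOL | Q2 | Q2 |

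With L = Q7 − (Q5 + Q6), SAP sWASO minus protocol sWASO is L, and SAP TIB minus protocol TIB is L. The end point cancels from sTST. At L = 0 the two columns are identical.

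**3. One illustrative night (assumed entries).** Tried to sleep 23:00, Q2 = 30, Q4 = 40, final awakening 06:00, Q6 = 15, out of bed 06:45. In minutes from 23:00, Q5 = 420 and Q7 = 465, so L = 465 − 435 = 30.

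- sWASO: 40 + 15 = 55 (protocol); 40 + 45 = 85 (SAP).
- Time in bed: 435; 465.
- sTST: 435 − 30 − 40 − 15 = 350; 465 − 30 − 40 − 45 = 350.
- sSE: 350/435 = 80.5%; 350/465 = 75.3%.

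The analysed value is a weekly mean, so sWASO for a visit moves by the mean of L over the nights used.

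**4. Change from baseline.** SAP change in sWASO = protocol change + change in L.

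- Constant L: the last term is zero and the sWASO change is the same.
- L differing by subject or visit: Var(SAP change) = Var(protocol change) + Var(change in L) + 2 Cov. The covariance may have either sign, so the variance may rise or fall.
- Mean change in L differing between arms by d: the treatment difference shifts by exactly d, in either direction.

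For sSE, a constant L only rescales. On an assumed 450-minute interval, the 5.5-point design difference becomes 5.5 × 450/(450 + L): 5.38 at L = 10, 5.32 at 15, 5.16 at 30 and 5.00 at 45.

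**5. Responder status.** A sleep maintenance responder needs a qualifying baseline, follow-up sWASO of at most 60 "minutes and shows a reduction of >10 minutes compared to Study Baseline". SAP 3.4.2.4 analyses "separately the subjects with sWASO > 60 minutes at the baseline for sWASO". With a constant L = 15:

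- Protocol-defined 90 to 50 is a responder. The SAP reads 105 to 65, which misses the follow-up cut-off.
- Protocol-defined 50 to 35 is outside the baseline set. The SAP reads 65 to 50, which is in the set, at or below 60 and down by 15: a responder.

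So a constant L can move subjects both ways across an absolute cut-off. Both examples hold whether the baseline limit is read as at least 60 (SAP 3.1.2) or above 60 (SAP 3.4.2.4).

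**6. What cannot be computed.** The documents give no mean, SD or arm contrast for L, so there is no basis for a corrected sample size or power.

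**The case against.** The best defence is that the protocol uses time in bed and trying to sleep loosely as one interval. Inclusion criteria 4, 8 and 11 describe time in bed as time spent either asleep or trying to be, and criterion 5 bounds the night by the attempt to sleep and by leaving bed. On that view Q7 simply puts the protocol's intention into practice. Equating the protocol end point with Q5 + Q6 is an inference, since the protocol prints no diary items. An unused Q6 proves little by itself: Q3 (number of awakenings) is also in no formula, and SAP Section 7 leaves derivation detail to separate documents.

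This has some force, but it does not reconcile the texts. The sWASO and sSE definitions name giving up on sleep, and the diary asks about that and about leaving bed in separate questions.

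A reader might go further and infer any of the following, none of which the documents support:

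- **An undisclosed late change.** The documents do not show when the Q7 formula was written, and SAP Section 5 claims to list only major changes after Amendment 03.
- **A loss of power or a bias in favour of the drug.** That needs a distribution for L and knowledge of what the SD of 43 contains. Neither is given, and step 4 shows that the effect could go either way.
- **A threat to the primary result.** sSOL is Q2 under both readings.

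**Conclusion.** The point holds as a disagreement between the two documents on how sSE and sWASO are derived, and it should be fixed. The mismatch in wording is clear; its impact is not known. It matters only on nights when L is not zero. It leaves sSOL and sTST untouched. If L is constant, it leaves the sWASO change untouched and rescales sSE slightly. The one consequence shown for a constant L is on sleep maintenance responder status, an endpoint with no multiplicity control. If L varies by subject, visit or arm, the key secondary comparisons are affected by an amount and in a direction that the documents do not allow anyone to state.

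The algebra assumes that stopping trying to sleep means Q5 + Q6. The night, the L values and the 450-minute interval are illustrations, not estimates.

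**What to change.** Before the Period 1 unblinding described in SAP Section 3, reconcile the passages to one derivation.

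1. **Follow the protocol:** in SAP 6.1.2 set sWASO = Q4 + Q6; TIB = (Q5 + Q6) − Q1; sTST = TIB − Q2 − Q4 − Q6; sSE = 100 × sTST/TIB. Or
2. **Keep Q7:** amend the protocol definitions of sWASO and sSE, and record the difference in SAP Section 5.

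Under either option, run the other derivation as a sensitivity analysis for sSE, sWASO and the sWASO responder endpoint.

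Add a data rule for nights on which Q5 + Q6 falls after Q7. SAP 3.3.5 says of impossible entries: "In such cases, erroneous data will be considered as missing values in data analyses". That should not be extended to these nights when Q7 is the end point. Q6 is a recalled duration, and discarding the night would throw away usable Q4, Q5 and Q7 and could push a week below the four-night minimum in SAP 6.1.1. Wherever Q6 is used, prespecify the handling, for example by capping Q5 + Q6 at Q7.

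One editorial correction belongs in the same edit. The protocol's sSE clause takes time asleep as time in bed minus sWASO and so omits sSOL. It should subtract both, as the SAP formula already does by including Q2.

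The cost is derivation wording in one document (a protocol amendment under option 2), the editorial correction to the protocol clause, one data rule, and sensitivity tables for three endpoints. All the diary items are already collected.

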9.5.1.3.2 INSOMNIA SEVERITY INDEX

The ISI is a 7-item, self-report questionnaire assessing the nature, severity, and impact of insomnia (Bastien et al., 2001). The dimensions evaluated are severity of: sleep onset, sleep maintenance, early-morning awakening problems, sleep dissatisfaction, interference of sleep difficulties with daytime functioning, noticeability of the sleep problems by others, and distress caused by the sleep difficulties. A 5-point Likert scale is used to rate each item (from 0=no problem to 4=very severe problem) yielding a total score from 0 to 28.

